5.2 Exclusion Criteria

Subjects will be excluded from participation if they meet **any** of the following criteria:

- a) The Subject has, in the opinion of the Investigator, a severe deformity that will hinder achieving a mechanical axis alignment target of $0^\circ \pm 3^\circ$.

- b) The Subject has, in the opinion of the Investigator, an existing condition that would compromise their participation and follow-up in this study.
- c) The Subject has, in the opinion of the Investigator, a flexion deformity that will not allow for 0° extension postoperatively.
- d) The Subject is a woman who is pregnant or lactating.
- e) The Subject, in the opinion of the Investigator, is a drug or alcohol abuser (in the last 5 years) or has a psychological disorder that could affect follow-up care or treatment outcomes.
- f) The Subject has participated in a clinical investigation with an investigational product in the last 3 months.
- g) The Subject is currently involved in any personal injury litigation, medical-legal or worker's compensations claims.
- h) The Subject has previous prosthetic knee replacement (any type including unicompartmental, total knee arthroplasty, patellofemoral arthroplasty or ipsilateral UTO/HTO) of the affected knee or a previous patellectomy.
- i) The Subject presents with ankylosis of the hip joint on the side to be treated.
- j) The Subject had a contralateral TKA and that knee was previously entered into the study.^B
- k) The Subject requires simultaneous bilateral total knee replacements.^C
- l) Any case in which Computer-Assisted Surgery (CAS) or TruMatch (or any other type of Custom Patient Instruments) is to be used, or any additional instrumentation are to be used for bone resections that are not provided as part of the ATTUNE RUI or SUI Instrument kits.
- m) The Subject requires a device not specified in the protocol or the surgeon determines that the ATTUNE Knee System is not a suitable treatment.

5.3 Definition of Subject Enrollment

As described in additional detail in Section 8.2 a patient will be considered **enrolled** when they have:

- ✓ Provided written informed consent to participate in this Investigation, which includes authorization of the release of their Personal Health Information (PHI).

B Having both knees from one Subject in the study could confound the data.

C As the study involves measuring the time taken for stages of surgery a simultaneous bilateral procedure would confound this dataset (would always take longer)

Confidential

Revision Date: 19Feb-2018

DePuy Synthes Joint Reconstruction
Protocol: CIP 10002 REV B

6 OBJECTIVES AND HYPOTHESIS

6.1 Primary Objective

To determine whether the mechanical axis alignment^D achieved with SUI instrumentation is non-inferior to the alignment achieved with RUI instrumentation. Mechanical axis alignment is defined as the line drawn from the center of the femoral head through the center of the knee and ankle and will be measured from weight bearing long-leg (51") Anteroposterior (AP) radiographs, taken approximately 90 days post-op (when subject has reached full knee extension) and read by an independent radiographic reviewer.

6.2 Secondary Objectives

- To compare alignment achieved with SUI vs. RUI of individual components in the frontal and sagittal planes, specifically: distal femoral varus-valgus (FM) , proximal tibial varus-valgus (TM), femoral component flexion and tibial slope.
- To compare the type and frequency of adverse events, from the time of surgery through to withdrawal of a subject or the end of the study (includes serious adverse events, and device and/or procedure-related adverse events), between the SUI and RUI instrument groups.

6.3 Exploratory Objectives

- To compare SUI and RUI operating room times from OR set-up through OR clean down as detailed in Table 8-3 of Section 8.3.3.
- To determine whether SUI provides opportunity to reduce the incidence of minor procedural obstacles during the time in the OR.
- To compare Surgeon satisfaction of SUI instrumentation to RUI instrumentation.

The primary and secondary clinical endpoints and the relevant statistical analyses are described in Section 10.6

6.4 Hypothesis

Hypothesis: If Single Use Instruments are used to implant an ATTUNE Total Knee, the alignment achieved will be non-inferior to that achieved with Reusable Instruments for the same procedure.

See Section 10.7 for further details on study hypotheses.

^D During preparation of this protocol discussions with the sites to be involved in this study confirmed that all 4 sites regularly plan to achieve $0^{\circ} \pm 3^{\circ}$ mechanical axis alignment. Exceptions to this are only in rare cases of extreme deformity. The study has therefore been designed with this in mind and collection of pre-operative plans are not required for the study.

7 STUDY DESIGN

This study is designed as a prospective, comparative, sequential, non-randomized, multi-center, controlled clinical investigation.

There will be 4 centers worldwide that will recruit a total of 88 Subjects (44 Treatment Subjects and 44 Control Subjects). A complete description of the methods for determining sample size is contained in Section 10.9. Initially, the Subjects will be evenly distributed across the four sites; therefore it is expected that each site will recruit 22 Subjects (11 Control followed sequentially by 11 Treatment Subjects). In between the Control and Treatment Subjects, a learning curve is permitted for the use of SUI.

- The **Control group** will consist of 44 Subjects, 11 per site and the surgical procedure for these Subjects will be performed using Reusable Instruments (RUI).
- The **Treatment group** will consist of 44 Subjects, 11 per site and the surgical procedure for these Subjects will be performed using Single Use Instruments (SUI).

At each site the 11 Control Subjects will be enrolled and operated on prior to performing the first surgery in the Treatment group. For a given site, either Cruciate Retaining or Posterior Stabilising configurations will be used; consistent with their standard of care. Within a given CR site, the Investigator may choose to implant either the CR FB or CR RP. Similarly, within a given PS site, the Investigator may choose to implant either the PS FB or PS RP. Randomization is not being applied in this study in order to isolate and learn if there are changes in OR efficiency with SUI under normal operating room procedures.

One surgeon at each site will complete all RUI and SUI surgical cases including the learning curve. No Sub-Investigators will be permitted to perform surgery to avoid possible confounding issues with varying surgical process. All sites will have previously completed their learning curve with the ATTUNE Primary Implant implanted using RUI prior to enrolling the 1st patient. Then after the completion of all RUI study cases, a learning curve will be permitted for the use of SUI. The duration of the SUI learning curve is anticipated to be approximately 5 cases and is at the discretion of the Principal Investigator. These early cases that are within the learning curve will not be enrolled into this study at each site.

Both resurfaced patellae and non-resurfaced patellae are permitted in this investigation, consistent with site standard of care. TruMatch technology or any other type of Custom Patient Instruments are not permitted. Similarly Computer-Assisted Surgery (CAS) is not permitted within the study. The procedures must be performed using only the instrumentation provided (SUI or RUI) and standard surgical methods, without additional tools that could confound the key research question of this study (for example, instrumentation that helps perform bone resections).

The Sponsor will monitor overall project enrollment. Cohort reallocation during the RUI phase only may be done in order to maintain project timelines. The Sponsor can authorize a shift of a group of Subjects from one site to another to maintain project timelines. For example, the Sponsor can reduce the cohort of a slow-enrolling RUI site to a faster-enrolling RUI site and the faster-enrolling RUI site will assume responsibility for the reallocated RUI cohort and the same number of SUI Subjects.

8 PROTOCOL

8.1 The sequence of events for a Subject are as follows:

- If the Patient is thought to be generally eligible, the Patient is invited to participate and the informed consent procedure is followed
- The Subject is screened for eligibility against the Protocol Inclusion/Exclusion criteria
- If the Subject meets the Protocol Inclusion/Exclusion criteria, a subject history is taken
- Within 180 days from initiating the consent procedure TKA surgery is performed during which operative details, timepoints of key stages of the procedure, instrument and device details, and any intraoperative complications are captured on eCRFs for submission and subsequent analysis.
- Approximately 90 days (+/-60 days) post-surgery weight bearing long-leg (51") Anteroposterior (AP) radiographs are taken and any postoperative complications collected. Radiographs are to be anonymized and sent to the Independent Radiographic Reviewer (IRR) for analysis.

8.2 Subject Enrollment

No study-related procedure or form associated with this study can be completed until written informed consent is obtained for that Subject. (see Section 5.3 Definition of Subject Enrollment).

8.2.1 Subject Screening

All Patients who present with NIDJD affecting the knee, and are candidates for primary, cemented TKA, and who generally meet the study requirements, will be screened for eligibility and will be listed on the Screening and Enrollment Log in order to document that the Subject selection was unbiased. The date of screening, the results of screening (included or not) and the primary reason for not including the patient (*e.g.*, does not satisfy eligibility criteria, not interested in participating) will be recorded on this log. The original log is to be retained at the Site and a copy sent to the Sponsor regularly during enrollment. A flowchart demonstrating the screening process and definition of enrollment is illustrated in Figure 8-1.

Eligible Patients who agree to participate in the study will be required to sign an Informed Consent Document prior to any study related procedures being done. ***After signing the Informed Consent, study Subjects are defined as "enrolled" and site will complete the non-standard of care pre-operative data collection.***

It is expected that complete data collection will be obtained for all enrolled Subjects, with the only exception being a Subject who is subsequently withdrawn. See Section 8.4 Discontinuation of Subject Participation (Withdrawal) for details.

8.2.2 Subject Informed Consent

In compliance with BS EN ISO 14155, and the Declaration of Helsinki, no Subject shall be enrolled in an investigation without provision of adequate informed consent. **The Principal Investigator is responsible for ensuring that no Subject is included in the study without adequate informed consent being provided.** Failure to obtain and properly document this process is in violation of BS EN ISO 14155, the Declaration of Helsinki, and this study protocol.

All informed consent documents (ICD) must have favorable opinion of the IRB/EC (Section 12.1). Consent of a Subject needs to be from the subject themselves and documented on an Informed Consent Document in the primary language of the Subject.

Screening, consenting and enrollment are illustrated in Figure 8-1. The Investigator or trained designee preliminarily screens to determine if a patient generally meets the eligibility criteria for the study (*item 2 in flowchart, Figure 8-1*). If so, the Investigator or trained designee shall offer study participation to those patients (*item 3 in flowchart, Figure 8-1*). If the patient agrees to participate s/he signs the informed consent document.

Table 8-1: Key Elements of Consent Process

Key Element of Consent Process (*item 4 of flowchart*)

The Investigator or designee shall confirm the Subject understands each of the following points of the study:

[figure not shown]
- The purpose of the study,
- The potential risks or adverse events that are posed by their treatment,
- The potential risks or adverse events directly related to study participation,
- Possibility of failure and the need for subsequent treatment(s),
- Alternative procedures/treatments available to the Subject,
- Requirements of the study including rehabilitation and follow-up visits,
- All of the Subject's rights as a participant in the clinical investigation.

Following the explanation of the study intent, the Investigator or trained designee shall offer to answer any of the Subject's questions. If the Subject then agrees to participate, his or her willingness must be documented via a signature and date on the IRB/EC's approved ICD and this document countersigned and dated by the person taking consent.

Upon successful completion of consent process, the Patient is enrolled and is identified as a Study Subject (*items 5 in flowchart, Figure 8-1*). The Investigator or trained designee will assess eligibility per Sections 5.1 & 5.2 (*item 6 in flowchart, Figure 8-1*).

Acquiring Consent on Day of Surgery: If the Informed Consent Document signatures are acquired on the day of surgery, a time stamp on the signature page is required to support that consent was obtained from the study Subject prior to any treatment related and/or mood altering medications being administered. A time stamp is not required where consent is obtained on a day prior to surgery.

Figure 8-1: Screening and Enrollment Process

8.2.3 Subject Identification Numbering

The **database assigns** Subject ID numbers after consent is obtained.

Each site is identified uniquely , e.g., 01-, 02- through 04, followed by 0001 for the first Subject, at the site, 0002 for the second Subject, and so on. For example, the first (3) three Subjects enrolled at Site #1 will be identified as 01-0001, 01-0002, 01-0003. Together the Site number and the Subject number will then become the unique identifier of the Subject and will be recorded on each page of the eCRF and on the Subject Screening & Enrollment Log.

In the instance of a Subject being enrolled, a number assigned and subsequently the Subject is deemed ineligible prior to receiving the ATTUNE knee, the Subject will be recorded as a screen failure on the screening/enrollment log. Once a Subject identification number is assigned, it may not be reused. Refer to Sections 8.4 Discontinuation of Subject Participation and 8.4.1 Enrollment Replacement Rules.

8.3 Study Procedures

This section is applicable to individuals who have undergone screening, have signed an Informed Consent Document, and have otherwise been found eligible to participate in this study per the Protocol’s Inclusion/Exclusion criteria. This section details the pre-operative, operative, and post-operative management of Subjects. Visit evaluations include radiographic evaluations. Sample Case Report Forms (CRFs) are located in Exhibit A. eCRFs must be submitted to DePuy Synthes Joint Reconstruction as outlined in Section 12.7 Case Report Form Completion and Data Submission.

8.3.1 Subject Evaluation Tools

No Patient Reported Outcome Measures are included in this study.

8.3.2 Pre-operative Management

Prior to surgery, the evaluations in Table 8-2 must be completed for each enrolled Subject. The interval for obtaining pre-op assessments is - 180 days to day 0 (day of surgery) as designated on the Time & Events Table 2.1. The pre-surgery management of each Subject enrolled in this investigation will be according to the standards of care used at the study site.

Table 8-2: Pre-operative Data Collection and eCRF

Evaluation	Details of Evaluation
Subject History	For all Subjects the Investigator or designee must confirm consent has been given, record the Subject’s demographic details and details of their previous medical history, and confirm eligibility on Subject History eCRF.
Radiographs	Pre-operative radiographs will be obtained.

8.3.3 Intra-operative Management

The surgical process is to follow site standard of care.

This investigation allows the Investigator to follow their current standard of care with respect to patellar resurfacing. Specifically the Investigator can choose to:

[figure not shown]
- Resurface the patella
- Leave the patella unresurfaced.

This investigation does NOT permit the Investigator to use TruMatch (or any other PSI instrumentation) or CAS for any Subjects, whether they are in the RUI or SUI arms of the study.

Products supplied by DePuy Synthes must be used in accordance with the manufacturer’s instructions unless an alternative technique is medically necessary.

Each Investigator or designee will collect information as noted in Table 8-3 below. The detailed surgical procedure is provided in Exhibit B. Data collection will begin at the time the OR is being set up for a study Subject procedure and will continue until the room is cleaned up and ready for the next case.

Table 8-3: Intra-operative Data Collection and eCRFs

Evaluation	Details of Evaluation
Operative Details eCRF	
For all Subjects, detailed surgical information and time information relating to the duration of 4 key elements of the surgical procedure will be recorded on the Operative Details eCRF. These 4 elements are OR Set Up, Anesthetic, Surgery & Clean Down. Definitions of each element will be provided as part of the training for individuals who will be capturing time data. Note there is likely to be overlap in time between some of these elements (possible scenario illustrated below).
  
In addition to the start and stop times for the 4 key elements, the occurrence of various incidents that can introduce delays or interruptions to the surgical flow will also be recorded.

Evaluation	Details of Evaluation
Device Log eCRF	For all Subjects , each component used during the procedure should be documented on the Device Log eCRF. The required product codes and catalog numbers can be found on pre-printed labels provided in the sterile implant boxes. Retain a copy of each label to facilitate data entry into the eCRF
Intra-operative Complications (if applicable) Adverse Event eCRF	In the event of an intraoperative complication , an Adverse Event eCRF is completed. An intra-operative complication is defined as a complication that occurs between the start of anesthesia and up to the time the Subject is moved to the recovery room. Complete a separate form for each intra-operative complication.

8.3.4 Post-operative Management

Immediate post-operative management is at the discretion of the Principal Investigator and should follow each Site's standard of care.

The one(1) postoperative study follow-up visit will be conducted according to the Time and Events Table 2.1. Each Investigator or designee will collect information as noted in Table 8-4 below. At this visit radiographs will be collected as detailed in the Radiographic Protocol (Exhibit F). An independent radiographic reviewer (IRR) will evaluate all radiographs. Copies of the evaluations will be available to Investigators upon request.

Table 8-4: Post-operative Data Collection and eCRFs

Evaluation	Details of Evaluation
Radiographs	For all Subjects post-operative radiographs will be obtained.
End of Study Completion or Subject Withdrawal	For all Subjects the Investigator or designee must complete an End of Study/Subject Withdrawal eCRF to confirm the Subject is no longer in the study.
Post-operative Complication(s) (if applicable)	In the event of a post-operative complication an Adverse Event eCRF is completed. A post-operative complication is defined as a complication that occurs at any time from the time the Subject is in the recovery room up through the time a Subject withdrawal form is submitted ending the Subject's study participation. Complete a separate form for each post-operative complication.

8.3.5 Radiographic Procedures

Weight bearing long-leg, hip-to-ankle (51" = 129.54 cm) Anteroposterior (AP) radiographs will be taken, as well as standard AP and lateral view radiographs, following the detailed instructions presented in the Radiographic Protocol (Exhibit F). While Patellar Skyline/Merchant view radiographs may be standard of care at some sites, they are not a requirement of the study and they do not need to be submitted to the IRR. All radiographs **must** be de-identified by the site prior to making them available for review by the Independent Radiographic Reviewer (IRR).

8.3.6 Management of Bias

To avoid potential bias and ensure consistency, an Independent Radiographic Reviewer (IRR) will be used to evaluate the post-op 90 day radiographs. This is an open investigation by design. Only the independent radiographic reviewer will be blinded regarding the instrumentation. The X-ray images will be provided with all Subject PHI information removed prior to assessment by the IRR. Data from the IRR radiographic evaluations (not the Investigators) will be used for determination of radiographic success criteria. Details of the radiographic assessment and means of submitting radiographs for review are detailed in Exhibit F, the Radiographic Protocol.

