10.2 Treatment Assignment

See Section 7.

Randomization will not be employed in this study. Each site will consecutively enroll all RUI cases prior to enrolling consecutive SUI cases.

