## 3 Randomization and Blinding Procedures

Neither randomization nor blinding will be implemented in this study.

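### PHI removal is the only stated masking of the radiographic reader; with all RUI cases before SUI at each site this does not secure the claimed blinding, and SAP section 3 says there is none

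*Protocol*

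**What the plan says.** Protocol 8.3.6 describes an open study with one exception: "Only the independent radiographic reviewer will be blinded regarding the instrumentation". It continues: "The X-ray images will be provided with all Subject PHI information removed prior to assessment by the IRR". Section 8.1 adds: "Radiographs are to be anonymized and sent to the Independent Radiographic Reviewer (IRR) for analysis". Section 8.3.5 likewise makes the site responsible for de-identifying films before review. For the details of assessment and submission, 8.3.6 points to Exhibit F, which is not among the supplied documents.

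SAP section 3 reads: "Neither randomization nor blinding will be implemented in this study".

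On numbering, Protocol 8.2.3 assigns a site prefix "followed by 0001 for the first Subject, at the site, 0002 for the second Subject, and so on". On the order of the arms, Protocol 10.2 states: "Each site will consecutively enroll all RUI cases prior to enrolling consecutive SUI cases". Sections 4.2 and 7 say the same, with about 5 unenrolled SUI learning cases between the two phases.

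**The concern.** The reader's hip-knee-ankle angle is the sole source of the primary endpoint (SAP 8.4.1), and the reader also supplies the secondary alignment angles (SAP 8.4.2). In an open, non-randomised study, 8.3.6 relies on this reader to guard against measurement bias.

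Taking out health information hides who the patient is. It does not by itself hide where the patient falls in a site's sequence, and here that position largely determines the arm. Two routes follow:

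- **Expectation.** A reader who can place a film early or late in a site's series can guess the instrument.
- **Trend.** If films are measured as they arrive, any change in landmark choice or technique over the study falls partly on the SUI minus RUI contrast.

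The analysis plan would not reveal either one. The only sensitivity analysis (SAP 8.7) repeats the primary test in a different population, and the supplied text describes no repeat reads.

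**Working it through.** **1. What the text settles.**

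| Question | Supplied text |
|---|---|
| Is the reader blinded? | Yes in Protocol 8.3.6; SAP section 3 says no blinding |
| Means of masking | Removal of health information, anonymization, de-identification (8.1, 8.3.5, 8.3.6) |
| Is the subject number on the film? | Not stated; 8.2.3 puts it on eCRF pages and the screening log |
| Are site and film date masked? | Not stated |
| Read on arrival or together, and in what order? | Not stated |
| Order of arms within site | All RUI, then all SUI (4.2, 7, 10.2) |
| Order of numbers within site | Sequential (8.2.3) |

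The last two rows together mean that, within a site, RUI numbers precede SUI numbers. The rows marked not stated decide whether this reaches the reader.

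**2. The plan's own power figure.** Inputs from Protocol 10.9: SD 1.87°, 35 per group, margin 1.5°, one-sided α = 0.05.

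- SE = 1.87 × √(2/35) = 0.447°.
- Noncentrality = 1.5/0.447 = 3.36 on 68 degrees of freedom.
- Power from the noncentral t is 95.3%, against 95% stated. The figure reproduces.
- With 44 per group, SE = 1.87 × √(2/44) = 0.399° and power is 98.2%.

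**3. What a reading bias would do.** The documents give no reader-repeatability figure, so the bias b in the mean absolute angle is an assumption. With the true difference at the margin and b favouring SUI, the chance of concluding non-inferiority is P(T > t₀.₉₅), where T is noncentral t with noncentrality b/SE. With no true difference and b against SUI, power uses (1.5 − b)/SE.

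| Assumed b | False non-inferiority, 35 / 44 per group | Power if b is against SUI, 35 / 44 per group |
|---|---|---|
| 0° | 5% / 5% | 95.3% / 98.2% |
| 0.25° | 13.8% / 15.3% | 86.9% / 92.9% |
| 0.5° | 29.5% / 34.4% | 71.6% / 80.1% |

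**4. How a constant drift feeds through.** The endpoint is |HKA − 180|, so a fixed shift in the signed angle does not pass one-for-one into the mean absolute angle. Assume normal signed angles with mean m and SD σ, with σ chosen so that the absolute value has SD 1.87°. The mean absolute angle is then σ√(2/π)·exp(−m²/2σ²) + m[1 − 2Φ(−m/σ)].

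- m = 0° (σ = 3.10°): a 0.5° drift either way raises the mean absolute angle by about 0.03°.
- m = 1° (σ = 2.94°): a 0.5° drift toward zero lowers it by about 0.10°. No constant drift lowers it by more than about 0.13°.

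Put into step 3 with 35 per group, b = 0.10° gives noncentrality 0.10/0.447 = 0.22 and a false non-inferiority rate of about 7.7%. A drop of 0.25° or 0.5° would need either a group already well off neutral or a reader who pulls SUI readings toward zero.

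**The case against.** A reader might infer that films reach the reviewer under the sequential subject numbers, that number and read order identify the arm, and that the blinding in 8.3.6 is therefore not delivered. The documents do not support that:

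- No section says the subject number is on the film. The text on films speaks of anonymization and de-identification.
- No section says films are measured on arrival. Labelling and read order would naturally sit in Exhibit F, and its absence here does not show that the safeguard is missing.
- The switch point is not a fixed number. Numbers lost to screen failure are not reused (8.2.3), withdrawn subjects are replaced (8.4.3), and cohorts can move between sites (section 7).
- Films are taken from day 30 to day 150 (10.4), and four sites can run at different speeds, so the arms can overlap in arrival time.
- Both arms receive the same implant (9.3), so the implant in the image does not show the arm.
- The larger error rates in the working do not describe ordinary landmark drift.

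All of this stands, and it limits the point to a safeguard that is not stated. It does not remove the point. Gaps and reallocation move the switch without breaking the order within a site. Overlap in film dates weakens the confounding without ending it. One could also read SAP section 3 as meaning only subjects and surgeons, but it makes no exception for the reader.

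**Conclusion.** The concern holds in a limited form, with moderate confidence. The measures in the supplied text do not secure the reader blinding that Protocol 8.3.6 claims, and SAP section 3 contradicts that claim as written. In a design where arm is nested in calendar time within site, inference of the arm and partial confounding with a reading trend are real risks. Neither is a documented fact.

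The size is unknown. The rates of about 14% and 30% (35 per group) rest on assumed differential biases of 0.25° and 0.5° in the mean absolute angle. They fit a reader influenced by knowing the arm better than they fit a constant drift, whose effect would usually be much smaller. The point is worth correcting because the remedy is cheap and the reader is the sole source of the primary endpoint. It does not show that the result will be biased.

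**What to change.** State the following in Protocol 8.3.6, the radiographic protocol (Exhibit F) and SAP section 3:

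1. Films go to the reader under random read codes, with subject number, site and film date masked. Data management holds the key.
2. Measurement reads take place after the last post-operative film is in, as one series in random order with RUI and SUI mixed. Image-quality checks on arrival may continue without measurement.
3. SAP section 3 says that subjects and surgeons are not blinded and the radiographic reviewer is, in agreement with 8.3.6.

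If Exhibit F already requires items 1 and 2, the remaining action is to correct SAP section 3.

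The cost is wording and a recoding list. The reader, the films and the number of reads stay the same. Measurements become available later, including the copies that investigators may request under 8.3.4.
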